9.7.1 Statistical Hypotheses

This registry is primarily descriptive and designed to detect potential safety signals, rather than test hypotheses.

9.7.2 Analysis of Demographics and Baseline Characteristics

Demographic and baseline characteristics will be summarized with simple descriptive statistics and data listings for the evaluable populations of pregnant women and live births. Demographic and baseline characteristics will also be summarized for the population that is lost to follow-up and compared with the evaluable populations to assess potential differences. These data will be reviewed for potential confounding factors that could affect the interpretation of comparisons of registry outcome rates with that of comparators. Further details will be provided in the SAP.

9.7.3 Statistical Methods

Overall and stratum-specific point estimates and 1-sided 95% confidence intervals will be calculated using the exact binomial distribution for prevalence rates of MCMs, preterm birth, and LBW among pregnant women exposed to Menveo and their live births. Most structural defects have their origins in the first trimester of pregnancy, the period of organogenesis. In addition to overall prevalence of MCM, the analysis of MCMs will be stratified by trimester of exposure to Menveo. The prevalence rate of combined MCMs reported to the registry will be calculated as a proportion with the number of MCMs as the numerator and the number of live births as the denominator, among women with first trimester exposure. Pregnancy losses with reported MCMs occurring at or after 20 weeks' gestation will be included in the numerator of the estimate of risk for MCMs to increase sensitivity and to allow comparison of outcomes with the CDC MACDP, which calculates rates by this convention. A secondary analysis will be conducted including pregnancy losses with reported MCMs occurring at less than 20 weeks' gestation in the calculation of risk. The prevalence rate of combined MCMs in exposed cases will be compared with that of the CDC MACDP ([Correa, 2007](#)).

Only cases meeting the CDC MACDP criteria for a defect or with 2 or more conditional defects will be included in the primary analysis. Single minor defects do not constitute a MCM according to the CDC MACDP classification; therefore, they will be listed in the report, but not included in the primary analysis.

The prevalence rate of preterm births and LBW will be calculated as proportions, with the number of live births as the denominator. These prevalence rates in exposed cases will be compared with those of the CDC NVSS ([Martin, 2012](#)). Because MCMs are often associated with preterm birth and LBW, infants with MCMs will be excluded from

analyses of these outcomes and will not be counted in the numerator or denominator when prevalence rates are determined.

The outcome data will be stratified by the earliest trimester of exposure to Menveo. For this registry, gestational weeks are estimated from the most reliable EDD as reported by the HCP. If a CEDD is provided by the HCP, it will be used instead. The date of conception will be calculated as the most reliable EDD minus 38 weeks. If the EDD is not available or never estimated, the first day of the LMP may be used to estimate gestational age. The second trimester will be considered to begin at week 14, and the third trimester, at week 28. If there is a discrepancy between gestational age calculated from LMP and reported gestational age, the HCP will be asked to verify the data.

If it is feasible, comparisons between the registry and an appropriate internal and/or external comparison group will be examined (see [Section 9.2.3.1](#) for a description of potential comparators).

Methods to Control for Confounding and Effect Modification

For analyses of associations between pregnancy outcomes and Menveo exposure, confounding and effect modification will be evaluated. A detailed description of these analyses will be available in the SAP. Potential confounders/effect modifiers may include the following:

- Maternal characteristics (e.g., age, ethnicity, race)
- Previous pregnancy outcomes (e.g., MCMs, stillbirth)
- Pregnancy complications (e.g., preterm labor, eclampsia, placental abruption)
- Comorbidities (e.g., diabetes, hypertension)
- Concomitant exposures (e.g., medications, alcohol, tobacco)
- Infant/fetus sex

Subgroup Analyses

Analyses will be stratified by trimester of exposure and other potential subgroups of interest, potentially including gestational age at enrollment and maternal age. Additional details on subgroup analyses will be described in the SAP. Comparisons may be made to external cohorts, if appropriate.

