9.2.3.1 Reference Groups

Given the inherent difficulties in identifying a comparison group (Covington, 2009), several different methods may be used to review the data for safety signals. As described below, background rates from external surveillance sources and rates from published literature will be the primary comparators. To the extent possible, comparator rates will be age-adjusted to reflect the age distribution of the Menveo Pregnancy Registry population.

Background Rates on Pregnancy Outcomes

Background rates in the general population on pregnancy outcomes, such as premature birth and LBW, are readily available from national vital statistics or publications in the scientific literature (Martin, 2012).

Background Rates on Congenital Anomalies

Published rates of MCMs are available from the Centers for Disease Control and Prevention (CDC)'s Metropolitan Atlanta Congenital Defects Program (MACDP), which is an ongoing population-based birth defects surveillance program (Correa, 2007). The primary objectives of MACDP are to regularly and systematically monitor births of malformed infants for changes in incidence or other unusual patterns suggesting environmental influences, and to develop a case registry for use in epidemiological studies. MACDP actively searches for MCMs among the 50,000 annual births to residents of metropolitan Atlanta's 5 counties and abstracts medical records at all Atlanta obstetric hospitals, Atlanta pediatric referral hospitals, genetics labs, and vital records (Correa-Villasenor, 2003). While there are inherent problems with comparing data from women exposed to specific vaccines in pregnancy with background rates from the general population, this is not an unrealistic comparison (Honein, 1999), and background rates may be the only practical comparator. MACDP has been used as a comparator by over 60% of pregnancy registries identified in a recent survey (Covington, 2009). When an analysis includes data from an external comparator, it is important to thoroughly

understand the methodology of the external comparator, and to take this into consideration when designing the analysis plan ([Kennedy, 2004](#)).

Background Rates from Literature or Other Studies

The registry is committed to identifying other appropriate comparison groups, and research of the literature and other sources, such as other pregnancy registries or observational studies, will continue in order to obtain appropriate background rates.

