9.3.2 Outcome(s) of Interest

MCM: The registry defines and codes MCMs with criteria specified by CDC MACDP ([CDC, 2007](#)). The registry defines an MCM as any major structural or chromosomal defect or combination of 2 or more conditional defects in live-born infants, stillbirths, or fetal losses of any gestational age (including outcomes prior to 20 weeks' gestation or birth weight <500 g). This definition is consistent with, but not restricted to, the CDC MACDP definition. Clusters of conditional abnormalities (as defined by CDC MACDP) and data from aborted fetuses of less than 20 weeks' gestation, when available, will be included to increase sensitivity of monitoring. The MACDP includes conditional defects only if in the presence of a major defect. This registry will consider reports of 2 or more conditional defects as a defect case, to increase signal sensitivity and to capture instances where a combination of conditional events might constitute a major defect or syndrome.

The registry conforms to the CDC MACDP guidelines in disqualifying as defects those findings that are present in infants born at less than 36 weeks of gestation and are attributable to prematurity itself, such as patent ductus arteriosus, patent foramen ovale, or inguinal hernias. The CDC MACDP classification does include chromosomal defects. Though these defects are not likely to contribute to a risk for a vaccine exposure, the registry includes these defects to maintain this consistency with the CDC MACDP.

Live-born infants with only transient or infectious conditions or with biochemical abnormalities will be classified as being without reported MCMs unless there is a possibility that the condition reflects an unrecognized MCM. Detected and reported transient or infectious conditions or biochemical abnormalities in infants without reported MCMs and defects that are excluded by the CDC guidelines will be noted in an appendix in the registry reports.

Preterm birth: An infant born at gestational age <37 weeks

LBW: An infant whose birth weight is <2500 g

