9.4.2 Operational Outcome Definition and Identification Process

All outcome variables will be provided by the obstetric HCP and/or pediatrician attending the birth. The HCP will be asked to describe any MCMs observed in the infant or fetus and will also be asked to report the gestational age and birth weight. These 2 variables will be used to calculate preterm birth (gestational age <37 weeks at birth) and LBW (birth weight <2500 g). A teratologist/geneticist will review all reported congenital anomalies and classify them using the CDC's MACDP system as specified in [Section 9.3.2](#). Additionally, the teratologist/geneticist will provide an opinion regarding the possible temporal association of the Menveo exposure to the development of observed defects. If additional information is needed to aid in classification or temporality assessment, the teratologist will request additional information using the targeted follow-up process outlined in [Section 9.4](#).

The SAC will meet periodically to review the data, discuss the MCM cases and their classification and temporality with the teratologist, and reach consensus on the coding and classification of MCMs and other primary endpoints.

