9.7.4 Statistical Considerations

Because early prenatal testing is so prevalent, it may be difficult to achieve adequate numbers of prospectively identified pregnant women if all pregnancies with prior prenatal

testing are excluded from the analysis. Therefore, the primary analysis will include pregnancies enrolled prior to outcome but after prenatal test as long as the test does not indicate an abnormality. However, this practice could potentially bias the results by lowering the overall risk of MCMs (Honein, 1999). The analysis will attempt to address bias introduced by this practice.

While the registry analysis will be limited primarily to prospective reports, some pregnancy exposures will be reported only following pregnancy outcome (retrospective cases). Each retrospective report will be carefully reviewed. In general, retrospective reports of exposures to vaccines or medication following notification of outcome are biased toward reporting of the severe and unusual cases and are not reflective of the general experience with the vaccine or medication. Moreover, information about the total number of exposed persons is not known. Therefore, rates of outcomes cannot be calculated from these data. However, a series of reported MCMs can be analyzed to detect patterns of specific MCMs and can identify early signals of vaccine or medication risks.

Those pregnancies that have reached EDD, but for which outcome information was unobtainable after 4 attempts, will be considered lost to follow-up. It is possible that outcomes among pregnancies lost to follow-up could differ from those with documented outcomes. Because of differences in individual reporting patterns, it is currently not possible to assess with any certainty what impact the potential biases the losses to follow-up may have on the analysis. However, efforts at comparing some of the characteristics of each group may be conducted in an attempt to address this potential source of bias.

Following the MACDP convention, calculation of MCM risk will exclude fetal losses (SABs, IABs, stillbirths, etc.) for which no MCMs have been detected as they may introduce a classification bias. The percentage of these pregnancies consisting of potentially normal outcomes or MCMs is unknown. The data collection form attempts to obtain information on MCMs detected at the time of the outcome. However, the reporting physician may not know the condition of the aborted fetus.

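### The primary MCM prevalence counts infants with two or more conditional defects and no major defect, but it is compared with a MACDP rate that does not count them

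*Protocol*

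**What the plan says.** Section 9.3.2 defines an MCM more widely than MACDP and says so. On MACDP's own rule it states: "The MACDP includes conditional defects only if in the presence of a major defect". The registry instead treats two or more conditional defects as a case on their own, to gain signal sensitivity. One sentence in that section announces two such widenings: "Clusters of conditional abnormalities (as defined by CDC MACDP) and data from aborted fetuses of less than 20 weeks" of gestation. The abstract carries the same wide definition.

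Section 9.7.3 fixes the primary analysis: "Only cases meeting the CDC MACDP criteria for a defect or with 2 or more conditional defects will be included in the primary analysis". It then sets the comparison: "The prevalence rate of combined MCMs in exposed cases will be compared with that of the CDC MACDP". Section 9.5 gives the reference rate as 2.54% for mothers under 25.

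For pregnancy losses, section 9.7.3 follows MACDP. Losses with MCMs from 20 weeks onward enter the numerator, partly so that the comparison can be made, and earlier losses go to a secondary analysis. The section makes no such separation for conditional-only cases.

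MCM status also feeds the other two primary outcomes: "Because MCMs are often associated with preterm birth and LBW, infants with MCMs will be excluded from" the preterm birth and LBW analyses (section 9.7.3).

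**The concern.** An infant with two conditional defects and no major defect is a case in the registry and not a case in MACDP. Reading one prevalence against the other mixes any vaccine effect with a difference in definition. Section 9.2.3.1 sets the opposite principle, that one should "understand the methodology of the external comparator, and to take this into consideration when designing the analysis plan". The protocol applies that principle to early losses but not to conditional clusters, and it gives no reason for the difference.

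With about 58 births the comparison rests on a handful of cases, so one case of a kind MACDP would not count can change how the result reads. Because MCM status removes infants from the preterm birth and LBW analyses, the definition also touches those outcomes, though only by the few infants concerned.

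**Working it through.** **Inputs.** n = 58 live births and p0 = 0.0254 (section 9.5); exact one-sample binomial, 1-sided 5% (section 9.6.2); exact 1-sided 95% limits (section 9.7.3). The protocol states no signal rule, so I take a signal to be a lower limit above 2.54%. The prevalence q of infants with two or more conditional defects and no major defect is not in the protocol. I assume q = 0.0025, 0.005 and 0.010.

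**Reproducing the protocol's figure.** The critical count is the smallest r with P(X ≥ r | 58, 0.0254) ≤ 0.05.
- P(X ≥ 4) = 0.0599 and P(X ≥ 5) = 0.0159, so r = 5.
- P(X ≥ 5 | 58, p1) = 0.80 gives p1 = 0.1132, and 0.1132 / 0.0254 = 4.46.

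This matches the 4.46-fold in section 9.5. That figure is correct for a numerator built on MACDP criteria.

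**How far one case moves the result.** The Clopper-Pearson 1-sided 95% lower limit for x cases is the 5th percentile of Beta(x, 58 − x + 1).
- 4/58: 2.39%, below 2.54%.
- 5/58: 3.46%, above 2.54%.

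Any fifth case would cross the line. The point is that a conditional-only fifth case would not be counted by MACDP.

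**Effect with no vaccine effect.** The registry's expected prevalence becomes p0 + q.

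| Assumed q | Expected extra cases, 58q | Expected ratio, (p0+q)/p0 | P(at least one), 1−(1−q)^58 | P(X ≥ 5), rate p0+q |
|---|---|---|---|---|
| 0 | 0 | 1.00 | 0 | 1.6% |
| 0.25 points | 0.145 | 1.10 | 13.5% | 2.3% |
| 0.5 points | 0.29 | 1.20 | 25% | 3.1% |
| 1.0 points | 0.58 | 1.39 | 44% | 5.4% |

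**What the wider numerator gains in power.** The true fold increase in MACDP-type defects detectable with 80% power is (p1 − q)/p0:
- (0.1132 − 0.0025)/0.0254 = 4.36
- (0.1132 − 0.005)/0.0254 = 4.26
- (0.1132 − 0.010)/0.0254 = 4.06

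Against 4.46, the gain in the MACDP comparison is slight.

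**The case against.** The strongest reply is that the choice is open and reasoned. Section 9.3.2 says the definition goes beyond MACDP and explains why, and the registry describes itself as descriptive and built to find signals, so an error toward over-detection suits its purpose. This justifies capturing and listing such cases. It does not justify reading them against a narrower rate, and the protocol nowhere says that the wider definition affects that comparison.

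The second reply is size, and most of it stands. The values of q are assumed, and at the two lower ones the false-signal chance stays below the nominal 5%. The step from four cases to five is also a selected illustration. Exactly four MACDP cases has null probability 0.0599 − 0.0159 = 0.044. Multiplied by the 13.5% to 44% chance of a conditional-only infant, this gives roughly 0.6% to 1.9%.

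Third, "A teratologist/geneticist will review all reported congenital anomalies and classify them", and the advisory committee discusses the MCM cases (section 9.4.2). Those reviewing individual cases could recognise a conditional-only one. The planned prevalence and its comparison would still include it.

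Fourth, other biases run downward. On enrolment after a normal prenatal test, section 9.7.4 says that "this practice could potentially bias the results by lowering the overall risk of MCMs". MACDP's active case finding (section 9.2.3.1) may also detect more than reports from health care providers do. Aligning the definition therefore does not by itself make the comparison like-for-like. But an upward bias of unknown size is not a correction for a downward one.

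Finally, the SAP was not available for this review and may add a MACDP-only analysis. The protocol nonetheless fixes the primary numerator and the comparison as described.

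**Conclusion.** The concern holds. By the protocol's own account of MACDP, the primary MCM numerator is wider than the comparator's, and no estimate on MACDP criteria is stated. This component of bias is zero or upward; the net bias of the comparison is unknown. Over an assumed q of 0.25 to 1.0 percentage points, the expected ratio with no vaccine effect is 1.10 to 1.39, and the false-signal chance is 2.3% to 5.4% instead of 1.6%. These figures rest on the assumed q and on reading the lower limit against 2.54%, neither of which the protocol supplies. The practical effect may be small, but the mismatch is avoidable and bears on the planned reading of a primary outcome.

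**What to change.** In section 9.7.3, base the comparison with MACDP only on cases that meet MACDP criteria. Report the wider definition, which adds two or more conditional defects, as its own prevalence and listing for signal detection, and state that it is not to be read against the MACDP rate. Once both are reported, state which one decides the exclusion of infants from the preterm birth and LBW analyses. Align section 9.3.2 and the abstract. The power statement in section 9.5 can stay as it is.

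The cost is a few wording edits and one extra reported row. No new data are needed, since section 9.4.2 already has every reported anomaly classified under MACDP. The one drawback is a slightly less sensitive numerator in the MACDP comparison; the wider row keeps that sensitivity for signal detection.
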